The clinical research team will perform a medical record review to acquire possible candidates for recruitment. The randomization scheme will be provided by the study biostatistician. Allocation will be concealed. Pharmacy will provide the medication or placebo. Randomization will be stratified in sex-specific tertiles (low, medium, high) defined by gastric emptying (T1/2, min).

Participants:

Subjects with obesity and abnormal satiety phenotype will be recruited by direct contact from an established database of patients or by public advertisement, including social media. All subjects will be given a verbal explanation of the study, provided time to read and study the written consent form and its information, and given opportunities to ask questions and copy the consent form. Participants will be informed of their right to withdraw from the study at any time without prejudice to their clinical management now or in the future. Consent will be sought by one of the medical doctor investigators or study coordinators, and consent will be documented by the participant's signature on the consent form virtually or in person. All recruitment or contact information will be approved by Mayo's Institutional Review Board.

Inclusion criteria:

- I. Patients with obesity $BMI > 30 \text{ kg/m}^2$ and hungry gut phenotype.
- II. Age: 18-65 years.
- III. Gender: men or women. Women of childbearing potential will have a negative pregnancy test before initiation of medication and within 48 hours of receiving radioisotope for the gastric emptying study.
- IV. Otherwise healthy individuals or with controlled chronic medical conditions such as type 2 diabetes.

Exclusion criteria:

- I. Structural or metabolic diseases/conditions that affect the gastrointestinal system, or functional gastrointestinal disorders. For screening the bowel disease questionnaire will be used to exclude subjects with irritable bowel syndrome.
- II. Subjects with stool type Bristol classification 6-7 per bowel disease questionnaire.

- III. Female subjects who are pregnant or breast-feeding.
- IV. Use of anti-obesity medications upon screening (ie., orlistat, phentermine-topiramate, liraglutide, semaglutide, bupropion-naltrexone), metformin or GLP-1 analogs.
- V. Individuals who are currently on treatment for unstable cardiac, pulmonary, gastrointestinal, hepatic, renal, hematological, neurological, endocrine, and psychiatric disease.

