- VI. Any acute or chronic condition or other disease that, in the opinion of the Investigator, would limit the subject's ability to complete and/or participate in this clinical study.
- VII. Significant untreated psychiatric dysfunction based upon screening. Hospital Anxiety and Depression Inventory (HAD) score >11 on depression scale, a self-administered alcoholism screening test (AUDIT-C) score >4 in men or >3 in women, and difficulties with substance or eating disorders determined by the Questionnaire on Eating and Weight Patterns (binge eating disorders and bulimia); will mean the participant will be excluded and given a referral letter to his/her primary care doctor for further appraisal and follow-up. The provider will review the patient's alcohol intake over the past few months to confirm accuracy and determine study eligibility.

VII. Principal Investigator discretion.

[figure not shown]
Intervention:

CBAS 500 mg tablets will be supplied by Bilarm Health Inc.. Subjects will take medication or placebo orally twice daily on an empty stomach, 30 minutes prior to breakfast and evening dinner for 90 +/- 5 days. Patients on the medication will receive 500 mg twice daily during their first week and 1000 mg twice daily for the rest of the study.

Methods:

Participants will keep food, appetite, and activity diaries for one week prior to baseline test day[11]. On randomization day they will also receive the randomized medication (delayed release IC-CBAS or placebo). A full medical history and physical exam will be performed and recorded, and a low-calorie diet will be suggested during this visit.

On Day 90 (+/- 5 days), subjects will repeat obesity phenotyping protocol at the exit visit [11] as described previously but will receive the study medication/placebo 30 minutes prior to the test meal.

*Visit 1, 3, 4 and 6 can be conducted at the Clinical Research and Trials Unit (CRTU)in the [REDACTED] at Mayo Clinic in Rochester, MN.

Visit 2 and 5 can be conducted at the CRTU or on [REDACTED]

Screening and Consent (virtual):

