Height, weight, blood pressure, heart and respiratory rates, waist and hip ratio, waist circumference, and temperature.
- Baseline and follow-up characteristics studies:
- Methods of metabolic studies:
 - o Body composition will be measured by DEXA (dual energy x-ray absorptiometry).
 - o Resting energy expenditure was assessed by indirect calorimetry with a ventilated hood (Parvo Medics, Sandy, UT).

- Gastric emptying (GE) of solids by scintigraphy [9] [8, 11] Images will be acquired at 0, 30, 60, 90, 120 and 240 minutes following the normal clinical gastric emptying testing protocol without a push meal.
- Satiation will be measured by *ad-libitum* meal to measure total caloric intake and macronutrient distribution in the chosen food. Satiation will be reported in calories consumed at fullness (satiation) [8] [11].
- Appetite sensations by visual analog score fasting and every 30 minutes after the standard meal for GE and the Satiation test up to 2 hours [8, 11].
- Blood samples: The fasting blood samples will be collected during the gastric emptying meal and stored at -70° C freezer. We will analyze plasma glucose, insulin, C-peptide, GLP-1, PYY₃₋₃₆, OXM, FGF-19, 7- α -C4, Adiponectin, Leptin, CCK, Pancreatic Polypeptide (PP), serum bile acids, short chain fatty acids, amino acids[2, 8]. Samples collection, handling, and storage: Samples will be collected after an overnight fast (of at least 8 hours) in the morning. Plasma will be preserved following standard guidelines and protein degradation inhibitors, kallikrein and DPP-IV inhibitors will be added to preserve the samples. Samples will be stored at -80°C in the PI's laboratory. Plasma hormones and proteomics by radioimmunoassay and/or mass spectrometry measured fasting, postprandial, and every 30 minutes for 6 hours. The primary endpoint being the peak postprandial level (test should be done simultaneously to GE).
- Blood DNA for genome wide association studies (GWAS). These samples will be stored for future research.
- Stool samples: One random stool will be collected at baseline and after treatment for fecal bile acids, short chains fatty acids and microbiome.
- Participants with childbearing potential will undergo a pregnancy test.
- Self-administered questionnaires assessing affect, physical activity levels, attitudes, body image, diet, and eating behavior; details of each questionnaire are provided below.

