- Participants will meet with the study team (either in person at the CRTU or virtually) approximately 30 days after visit 2. The study team will assess adverse events, medication compliance, and perform a new medication dispensation (if visit is virtual the medication will be shipped to the participant's preferred address).

- **Visit 4: Study Team visit**

Participants will meet with the study team (either in person at the CRTU or virtually) approximately 30 days after visit 3. The study team will assess adverse events, medication compliance, and perform a new medication dispensation (if visit is virtual the medication will be shipped to the participant's preferred address).

- **Visit 5: Colonoscopy #2**

- Visit 5 will only be completed in the first 6 patients of each group who are willing to consent to both colonoscopy visits.
 - Participants will receive a bowel prep (Movi-prep) during visit 5 and follow standard colonoscopy preparation guides. The next day, after an overnight fasting, a colonoscopy with terminal ileum intubation will be performed. The colonoscopy will be done in the GI clinical or research unit and will be supported by sedation based on patients' characteristics (i.e., conscious sedation vs. anesthesia supported sedation). During the procedure, 8 biopsies will be obtained from the ilium, right and left colon.

- **Visit 6 – Exit Phenotyping**

- Visit 6 will occur within 7 days of Visit 3. Phenotyping will be performed as at the baseline phenotyping visit including the questionnaires performed in screening visit.

Primary Endpoint:

The primary endpoint is EEC function measured through satiety hormones' (GLP-1 & PYY AUC and absolute plasma value curves) comparison between intervention and placebo groups at day 90 in APS-OB phenotype participants.

Secondary Endpoint:

Evaluation of obesity phenotypes through gastric emptying T_{1/2} for solids, satiety sensation with a visual analogue scale (VAS), fullness (VAS), hunger (VAS), desire to eat (VAS), appetite overall score (VAS), ad-libitum buffet meal food intake (kcal), microbial changes, behavioral questionnaires, energy expenditure, and body weight in APS-OB phenotype participants intervened with IC-CBAS, compared to placebo.

Statistical Analysis:

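### Controlled type 2 diabetes is admitted and GLP-1 analogs are excluded, but DPP-4 inhibitors are not, in a trial whose primary endpoint is plasma GLP-1 and PYY

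*Combined protocol and SAP*

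**What the plan says.** Inclusion criterion IV accepts "Otherwise healthy individuals or with controlled chronic medical conditions such as type 2 diabetes". Exclusion criterion IV reads "Use of anti-obesity medications upon screening (ie., orlistat, phentermine-topiramate, liraglutide, semaglutide, bupropion-naltrexone), metformin or GLP-1 analogs". DPP-4 inhibitors do not appear there or in any other criterion.

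Three other exclusions might be thought to cover them:

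- Exclusion V applies to "Individuals who are currently on treatment for unstable cardiac, pulmonary, gastrointestinal, hepatic, renal, hematological, neurological, endocrine, and psychiatric disease". Diabetes that is treated and controlled passes it.
- Exclusion VI concerns conditions that limit a person's ability to complete or take part in the study.
- The last item, "Principal Investigator discretion", permits removal case by case but names no drug.

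The Primary Endpoint section defines the outcome as enteroendocrine cell function, measured through "GLP-1 & PYY AUC and absolute plasma value curves" at day 90. The only mention of DPP-IV inhibitors is under Visit 1, blood samples: "kallikrein and DPP-IV inhibitors will be added to preserve the samples".

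Randomization is stratified by sex-specific gastric emptying category (Research Plan, and Visit 2). The ANCOVA in Statistical Analysis adjusts for gastric emptying and gender.

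**The concern.** The eligibility rules remove one incretin-related drug class from a hormone-endpoint trial and leave open another, which is named for the very enzyme that the laboratory procedure inhibits to protect the samples. A participant with controlled diabetes who takes such a drug is eligible as the text stands.

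If the drug alters that person's measured GLP-1 or PYY, the alteration enters the primary comparison as noise. With 18 per arm planned and 12 per arm assumed to complete, one or two people have visible weight in an arm mean. Nothing in the allocation or the model separates them out. Baseline hormone level is not listed as a covariate either, so a stable user's shift would not be removed by baseline adjustment.

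**Working it through.** The plan states no figure on this point, so there is none to reproduce. The check has a textual part and a sizing part.

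**Text.** Controlled type 2 diabetes is allowed (inclusion IV). Metformin and GLP-1 analogs are excluded (exclusion IV). DPP-4 inhibitors are not named, and no other criterion sets a rule for them. No washout, stable-dose or concomitant-drug rule appears elsewhere. The gap is real.

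**Inputs from Statistical Analysis.** Planned difference 3223, SD 3125 (units as printed), 12 per group needed, 36 enrolled to allow for up to 30% dropout. Hence n = 18 per arm at entry and n = 12 per arm as planned completers.

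**Assumptions, because the documents give no values.** A user's AUC shifts by s times 3223, with s from 0.5 to 2. One arm has k more users than the other.

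**Shift of the contrast**, as a share of 3223: k × s / n.

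| k | n | s = 0.5 | s = 2 |
|---|---|---|---|
| 2 | 18 | 2 × 0.5 / 18 = 5.6% | 2 × 2 / 18 = 22.2% |
| 2 | 12 | 2 × 0.5 / 12 = 8.3% | 2 × 2 / 12 = 33.3% |
| 1 | 18 | 2.8% | 11.1% |
| 1 | 12 | 4.2% | 16.7% |

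**Yardstick: standard error of the planned contrast**, SD × √(2/n).

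- n = 12: 3125 × √(2/12) = 1276, and 1276 / 3223 = 40%.
- n = 18: 3125 × √(2/18) = 1042, and 1042 / 3223 = 32%.

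The worst assumed shifts are therefore 33.3 / 39.6 = 0.84 of a standard error at 12 per arm and 22.2 / 32.3 = 0.69 at 18 per arm.

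**How easily the imbalance arises.** If exactly two of 36 participants were users, simple 18:18 allocation (ignoring the strata) would put both in the same arm with probability 17/35 = 49%.

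**The same effect seen as variance.** Suppose instead that a share p of participants are users and each shifts by m SDs. The SD becomes 3125 × √(1 + p(1 − p)m²).

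- p = 10%, m = 0.5: 3125 × √1.0225 = 3160.
- p = 30%, m = 2: 3125 × √1.84 = 4239.

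Two-sided 5% t-test power at 12 per group goes from 67.5% with SD 3125 to 66.6% and 42.9% respectively. The starting value is 67.5% rather than the stated 80% because 12 per group does not give 80% power in a two-sided 5% test. That is a separate matter. This calculation also assumes that 3125 contains no contribution from users, which the documents do not establish. It describes the same noise as the imbalance calculation, so the two should not be added.

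**The case against.** Several stronger readings are tempting, and the documents do not support them.

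- **The treatment effect would be biased.** Randomization prevents systematic bias from use at baseline. Chance imbalance is part of ordinary sampling error, and the worst assumed case is under one standard error. This objection stands.
- **Users' hormone levels would be set by the drug.** The blood-sample paragraph lists more than a dozen analytes and does not say which ones the preservative protects. It says nothing of what an oral drug does to GLP-1 or PYY AUC at day 90, nor whether the assay is total or active. Size and direction cannot be fixed from the documents. This stands.
- **Excluding metformin and GLP-1 analog users makes DPP-4 inhibitor users likely.** It equally raises the share of people with diabetes who take no drug. The trial describes its population as otherwise healthy, and the number of users could be zero. This stands.
- **The SD would exceed the planned value.** The planning SD comes from the earlier trial, which the protocol describes as a trial in type 2 diabetes. It may already reflect such use. This stands.
- **The words about screening leave use uncontrolled.** Eligibility is normally judged at entry, so this wording adds little.
- **Recording is missing.** The Design section provides a medication diary, the Baseline phenotype section has medication use entered weekly, and the history form has a medication field. Recording therefore largely exists.

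What remains is narrower. The class is not named, investigator discretion is not a prespecified rule, and the design does nothing to absorb the noise if users enrol.

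**Conclusion.** The point holds as a cheap tightening of one criterion. It is not a threat to the validity of the comparison. The eligibility text leaves open a drug class that bears on the enzyme the protocol inhibits when handling samples for its primary endpoint. The consequence is possible extra variance and chance imbalance in a 36-person trial.

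Under the stated assumptions, two users in one arm and none in the other move the contrast by 6-22% of 3223 at 18 per arm or 8-33% at 12 per arm. The lower end is negligible. The upper end is noticeable but within one standard error. All of this rests on an assumed shift of 0.5 to 2 times the planned difference and on assumed user counts.

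A reader might infer that the primary result would be biased or that users are likely to be common. Neither follows from the text. Drugs started during the 90 days differ from baseline use. Randomization does not protect against them, because starting could depend on glycemia and so on assigned treatment.

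**What to change.** Add DPP-4 inhibitors to exclusion criterion IV next to GLP-1 analogs. This is an eligibility change only and asks nobody to alter treatment. If the sponsor prefers to admit users, the plan should say so and state how they will be analysed.

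Use the existing medication diaries to identify any start of these classes during the 90 days. Check that the weekly form captures them, since the diary summary in Appendix A shows dose fields (Dose 1 and Dose 2) but none for other drugs.

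Keep all randomized participants in the primary analysis. An analysis without on-study starters may be prespecified, but only as supportive, because it excludes people after randomization and could introduce bias that the main analysis does not have.

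Cost: a few words in one criterion, and a few candidates with type 2 diabetes become ineligible.

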This is a single-center, placebo-controlled, double-blinded, parallel-group, randomized 90 days (+/- 5 days) trial to study the effect of IC-CBAS 500 mg and 1000 mg BID on EEC function, satiety perception, body weight and satiety GI hormones, in patients with APS-OB phenotype. A lifestyle intervention will be provided. These consist of an obesity physician consult, a low-calorie diet instructed by a member of the study team, and physical activity and behavioral suggestions. These interventions should last at least the length of the study. In addition, this study will include 2 colonoscopies at the beginning (i.e., before medication/placebo start) and at the end of the study (i.e., after last dose of medication/placebo) in the first 6 patients in each group willing to consent to the colonoscopies (12 patients; 24 colonoscopies in total). Participants will receive a bowel prep (Movi-prep) and follow standard colonoscopy preparation guides. The next day, after an overnight fasting, a colonoscopy with terminal ileum intubation will be performed. The colonoscopy will be done in the GI clinical or research unit and will be supported by sedation based on patients' characteristics (i.e., conscious sedation vs. anesthesia supported sedation). During the procedure, 8 biopsies will be obtained from the ilium, right and left colon. We will include otherwise healthy patients with a BMI > 30 kg/m², age range 18-65 years, and APS-OB phenotype. Based on the results of our previous trial comparing weight loss in exenatide therapy vs placebo [2], we calculated a sample size of 18 participants per group (total of 36) with 80% power, 0.05 alpha to detect a 1 kg difference between treatment and placebo groups.

Study Intervention:

Ileocolonic-release conjugated bile acid 500mg tablets will be provided by Bilarm Health Inc., San Diego, CA.

Anticipated Results:

In comparison with placebo, IC-CBAS will result in improved EEC function, increased postprandial incretin secretion, and weight loss when compared to placebo.

Significance:

We expect to demonstrate that delayed IC-CBAS increases satiety, restoring satiety in patients with APS-OB phenotype. This study will provide the basis for future pharmacological studies, exploring the effect of luminal enteroendocrine secretagogues in patients with obesity and APS-OB phenotype.

BACKGROUND:

Overview:

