We propose a single center, placebo-controlled, randomized double blinded 90 (+/- 5) day trial, to study the effect of IC-CBAS delivery (500 mg BID for the first week and 1000 mg BID for the rest of the study) on colonic EEC function, postprandial incretins (GLP-1, PYY₃₋₃₆, FGF-19, and OXM), body weight, and satiety (evaluated with gastric emptying and appetite based VAS) in patients with obesity and abnormal satiety. We plan to randomize 18 participants per group. Participants will complete the following visits: 1) Screening and Consent (virtual); 2) Baseline phenotype, lifestyle intervention, 3) Colonoscopy and Randomization visit prior to medication start (in first 6 patients in each arm) who are willing to consent to colonoscopy), 4) Two (in person or virtual) Study Team visits at 30 & 60 days post randomization, 5) Colonoscopy visit and 6) Exit Phenotype visit after taking last medication dose (in first 6 patients in each arm). During the phenotype visits, participants will be phenotyped by measuring energy expenditure, satiety with gastric emptying of solids and VAS scores, satiation with calories consumed to fullness, and emotional eating by questionnaires[8]. Resting energy expenditure will be measured by indirect calorimetry, gastric emptying will be assessed with scintigraphy and calories to fullness will be tested in *ad libitum* meal. In addition, participants will have a body composition with a DEXA scan. Blood will be collected every 30 minutes for 6 hours and selected plasma gastrointestinal hormones will be measured. A sample will be stored for venous blood DNA analysis. Stool samples will be collected for 24 hours for microbiome, bile acids and short chain fatty acids. Participants will keep a food, medication, and activity diary. Participants

will receive a bowel prep (Movi-prep) and follow standard colonoscopy preparation guides. The next day, after an overnight fasting, a colonoscopy with terminal ileum intubation will be performed. The colonoscopy will be done in the GI clinical or research unit and will be supported by sedation based on patients' characteristics (i.e., conscious sedation vs. anesthesia supported sedation). During the procedure, 8 biopsies will be obtained from the ilium, right and left colon. During the Study Team visits, patients will meet with the study team to review medication compliance, assess adverse events, and perform a medication dispensation.

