All participants will meet with a study physician as standard of care in clinical practice. All participants will guided to 1) Diet: Reduce dietary intake below that required for energy balance by consuming 1200 calories per day for women and 1400 calories per day for men; 2) Physical Activity: reach the goal of 10,000 steps or more per day; 3) Exercise: reach the goal of 150 minutes or more of cardiovascular exercise/week; 4) Limit consumption of liquid calories (i.e. sodas, juices, alcohol, etc.).

- **Visit 2: Colonoscopy #1 and Randomization**

- Visit 2 will only be completed in the first 6 patients of each group who are willing to consent to both colonoscopy visits.
- Visit 2 will occur 3- 5 days of Visit 1. Participants will receive a bowel prep (Movi-prep) during Visit 1 and follow standard colonoscopy preparation guides. The next day, after an overnight fasting, a colonoscopy with terminal ileum intubation will be performed. The colonoscopy will be done in the GI clinical or research unit and will be supported by sedation based on patients' characteristics (i.e., conscious sedation vs. anesthesia supported sedation). During the procedure, 8 biopsies will be obtained from the ilium, right and left colon.
- Randomization and treatment:
Randomization will be performed by the research pharmacy upon notification by the study coordinator. Treatments will be allocated at a 1:1 ratio stratified within low, medium, or high gastric emptying (T1/2) rates, based on sex-specific thresholds. The stratification group will be determined by the study coordinator and communicated to the pharmacist. A computer application will provide the randomized assignment based on a randomization schedule created by the study statistician. Only the study statistician will have access to the complete schedule. Other study personnel and the subject will be blinded to assigned treatment.

Patients will receive study medication (active or placebo), and they will be given verbal instructions on how they should take their medications. Subjects will take medication or placebo orally twice daily on an empty stomach, 30 minutes prior to breakfast and evening dinner for 90 (+/- 5) days. Patients will be instructed to start the medication after visit 2 (colonoscopy).

- **Visit 3: Study Team visit**

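### Does limiting colonoscopy to the first 6 consenting patients of each group need a change, when randomization falls in the same visit?

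*Combined protocol and SAP*

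**What the plan says.** The Study design section places two colonoscopies "in the first 6 patients in each group willing to consent to the colonoscopies (12 patients; 24 colonoscopies in total", the first of them "i.e., before medication/placebo start". The Design section of the Research Plan lists a "Colonoscopy and Randomization visit prior to medication start (in first 6 patients in each arm", and states "We plan to randomize 18 participants per group". Under Visit 2 the restriction reads "Visit 2 will only be completed in the first 6 patients of each group who are willing to consent to both colonoscopy visits", and Visit 5 repeats it for the second colonoscopy.

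On allocation, the Design section says "Randomization will be stratified in sex-specific tertiles (low, medium, high) defined by gastric emptying (T1/2, min". Under Visit 2, the research pharmacy randomizes when the coordinator notifies it, and the coordinator determines the stratum. The full schedule is open to the statistician alone, and other personnel are blinded. Bowel preparation is handed out at Visit 1, and Visit 2 falls 3 to 5 days later.

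On timing, Visit 2 has medication starting after that visit, and Visit 3 is set about 30 days after Visit 2. The Design section instead has "Study Team visits at 30 & 60 days post randomization", and Methods says "On randomization day they will also receive the randomized medication (delayed release IC-CBAS or placebo".

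**The concern.** A rule that takes the first 6 of each group presupposes that the group is known. Yet randomization sits in the same visit as the colonoscopy, bowel preparation is given out a visit earlier, and the staff who run the visits are blinded. The protocol does not say whether the draw comes before or after patients are chosen and scoped, nor who counts places by arm. Colonoscopy consent is not a stratification factor, so nothing in the schedule makes 12 consenters fall 6:6.

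Two things could be at stake. One is sedated colonoscopies beyond the planned 24. The other is concealment: once one arm is full, a consenter who is turned away is in the full arm and a later one who is scoped is in the other. The coordinator who might see this also requests each randomization and sets its stratum.

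A second worry is textual. Visit 2 contains randomization and first dispensing but is limited to the colonoscopy subset. Read literally, most participants have no randomization visit and no start for the 30-day count.

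**Working it through.** **The plan's own figures.** 6 per group × 2 groups = 12 patients; 12 × 2 colonoscopies = 24. Both agree with the Study design section.

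**Would 12 consenters, taken regardless of arm, split 6:6?**

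- Simple 1:1 allocation: C(12,6)/2^12 = 924/4096 = 22.6%.
- 12 drawn at random from 18 + 18: C(18,6)²/C(36,12) = 27.5%.
- Permuted blocks within strata, by simulation (36 participants, 40,000 runs per setting). The protocol gives no block size or consent rate, and sex-specific tertiles can be read as 3 or 6 strata. These are therefore assumptions, shown as a range. Results are for runs with at least 12 consenters; mean scoped further requires both arms to reach 6.

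| Strata | Block | 6:6, all consent | 6:6, half consent | Mean scoped until both arms have 6 (all / half) |
|---|---|---|---|---|
| 3 | 2 | 62.4% | 30.9% | 12.4 / 13.4 |
| 3 | 4 | 50.2% | 30.4% | 12.7 / 13.5 |
| 3 | 6 | 40.4% | 30.0% | 13.0 / 13.5 |
| 6 | 2 | 45.4% | 30.3% | 12.9 / 13.5 |
| 6 | 4 | 34.3% | 28.5% | 13.3 / 13.6 |
| 6 | 6 | 28.5% | 27.9% | 13.7 / 13.6 |

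A split of 8:4 or worse occurs in 0–28.4% of these runs, so stopping at 12 gives 7:5 or closer in about 72–100%. Without a per-arm count, exact balance is therefore not assured.

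**What does enforcing the count cost?** In a companion simulation (3 or 6 strata, blocks of 2 or 4, 50–100% consent), at least one consenter is turned away because of arm in about 38–70% of runs. The mean number turned away is 0.4–1.8. Each misses an optional research colonoscopy, and no colonoscopy is added to the 24.

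**Can the count be kept with the blind intact?** Put the steps in order:

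1. Gastric emptying, which sets the stratum, is measured at Visit 1.
2. Visit 2 follows 3 to 5 days later, and the only stated constraint is that colonoscopy precedes medication.
3. The pharmacy randomizes and supplies active drug or placebo, so it can tally consenters by arm as they are assigned.
4. It can draw between the two visits and return only whether to scope. Holding a bowel preparation kit does not commit a participant to the procedure.

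If willingness is recorded before the draw, the first 6 in each arm remain comparable samples of consenters.

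**Which listed results are affected?** The Primary Endpoint is GLP-1 and PYY in plasma. Neither the Secondary Endpoint list nor the Statistical Analysis section names a biopsy outcome.

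**The Visit 2 wording.** Literally, 36 − 12 = 24 participants lack a Visit 2. But the Design section randomizes 18 per group and counts the 30- and 60-day visits from randomization, and Methods describes a randomization day with dispensing for participants in general. The restriction can only sensibly apply to the colonoscopy part of the visit.

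**The case for a change.** The best case for acting is that the missing step is easy to supply and has some bearing on concealment. Under the assumed settings, 1.9–4.0 consenters on average arrive while exactly one arm is full. If staff see who is scoped, some of these can be grouped by arm. At 50% consent both arms reach 6 in only about 90% of runs, although 12 consenters exist in about 98.5%. A separate balanced list for the first 12 consenters would give 6:6 whenever 12 people consent, with nobody refused because of arm.

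Part of this stands. The order of draw and selection is unstated, and no role is named to keep the tally. But the grouping shows only same arm or other arm, not active or placebo, and it requires slot decisions to be visible. The 1.9–4.0 also includes people accepted into the open arm; those refused average 0.4–1.8.

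The separate list has its own price. It removes gastric emptying stratification for 12 of 36 participants, and the mean arm difference within a stratum rises from 0.5–0.7 to 1.1–1.5 participants. Covariate adjustment may not make this good for the primary comparison, which is sized as a two-sample t-test; the ANCOVA is described for weight loss and the remaining endpoints, though that list includes GI hormones. Stopping at the first 12 consenters whatever their arm avoids that price but gives up the 6 per arm the protocol asks for, and improves no listed result.

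**Conclusion.** No change follows. The rule can be run as written by a pharmacy draw between Visits 1 and 2, and the unstated order and tally are operational details that the study team can settle sensibly. The stratification alone would not secure 6:6 (about 28–62% under the assumed blocks, strata and consent rates, 23–28% without stratified blocks), but the per-arm count is there for that purpose and costs on average 0.4–1.8 refused optional procedures. What remains is a small exposure of arm grouping if slot decisions are visible, and a chance of about 10% at 50% consent that one arm falls short of 6. Neither touches a listed endpoint, the sample size or an analysis. Each alternative trades away stratification or the intended balance. The Visit 2 restriction is a clerical slip that the Design and Methods sections already resolve for the other 24 participants.

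This rests on two readings: that the pharmacy knows each assignment as it is made, and that willingness is recorded before the draw. The probabilities rest on the assumed allocation settings and on consent being independent of arm.
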